## 6.2 DATA SHARING PLANS

### 6.2.1 Human Data Sharing Plan

#### What data will be shared?

I will share human data generated in this research for future research as follows:

- De-identified data in an NIH-funded or approved public repository.
- De-identified data in BTRIS (automatic for activities in the Clinical Center)
- De-identified or identified data with approved outside collaborators under appropriate agreements.

#### How and where will the data be shared?

Data will be shared through:

- An NIH-funded or approved public repository. Insert name or names: ClinicalTrials.gov.
- BTRIS (automatic for activities in the Clinical Center)
- Approved outside collaborators under appropriate individual agreements.
- Publication and/or public presentations.

#### When will the data be shared

- Before publication.
- At the time of publication or shortly thereafter.

## **6.3 RESPONSE CRITERIA**

### **6.3.1 Definitions**

Evaluable for toxicity: All patients will be evaluable for toxicity from the time of E6 TCR T cell infusion. Toxicity data will be collected for all patients.

Evaluable for objective response: Only those patients who have measurable disease present at baseline, have received an E6 TCR T cell infusion, and have had their disease re-evaluated for response will be considered evaluable for response. These patients will have their response classified according to the definitions stated below.

### **6.3.2 Disease Parameters**

Measurable disease: Measurable lesions are defined as those that can be accurately measured in at least one dimension as  $\geq 5$  mm. All measurements must be recorded in millimeters (or decimal fractions of centimeters).

Non-measurable disease. All other lesions (or sites of disease), including small lesions (longest diameter  $< 5$  mm), are considered non-measurable disease.

Target lesions. All measurable lesions will be identified as target lesions and recorded and measured at baseline.

Non-target lesions. All other lesions (or sites of disease) will be identified as non-target lesions and should also be recorded at baseline. Measurements of these lesions are not required, but the presence, absence, or in rare cases unequivocal progression of each will be noted throughout follow-up.

### **6.3.3 Methods for Evaluation of Measurable Disease**

Lesions will be photographed, described in detail, and measured at each response evaluation. Measurements will be recorded in metric notation using a ruler or calipers. Baseline evaluations will be performed no more than 8 weeks before starting treatment.

The same method of assessment will be used to characterize each identified and reported lesion at baseline and during follow-up. Lesions will be documented by digital color photography at each response evaluation.

### **6.3.4 Response Criteria**

#### **6.3.4.1 Evaluation of Target Lesions**

Complete Response (CR): Disappearance of all target lesions. No appearance of new lesions.

Partial Response (PR): A  $\geq 50\%$  decrease in the sum of the product of the longest perpendicular diameters of target lesions, taking as reference the baseline measurements. No appearance of new lesions. No increase of greater than 25% of any index lesion.

Progressive Disease (PD): A  $\geq 25\%$  increase in sum of the product of the longest perpendicular diameters of target lesions, taking as reference the smallest product on study (this includes the baseline product if that is the smallest on study). In addition to the relative increase of 25%, the sum must also demonstrate an absolute increase of at least 5 mm. (Note: the appearance of one or more new lesions is also considered progression).

Non-CR/Non-PD: Neither sufficient decrease to qualify for PR nor sufficient increase to qualify for PD, taking as reference the smallest product of diameters while on study.

Note: In the event of lesion regression with a residual abnormality of unclear significance, a biopsy may be obtained. If HSIL is present in the pathology specimen the response will be considered less than complete. If HSIL is not present the response will be considered complete.

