#### 3.5.1 Evaluation:

- Patients will follow up 1 and 2 weeks after cell infusion for safety assessment and research studies as indicated on the **Study Calendar**. Response will not be measured at these visits.
- Patients will follow up 1, 2, and 3 months after cell infusion for safety assessment, research studies, and response evaluations.
- Patients with no response at the 3 month evaluation will come off-treatment and receive standard of care therapy.
- Patients with a partial or complete response at the 3-month evaluation will follow up at 4, 5, and 6 months for safety, response, and research evaluations.
- After the 6-month response assessment patients with partial response will receive standard of care therapy. Patients with a complete response will thereafter have follow-up every 3 months (+/- 30 days) for 2 visits, then every 6 months (+/- 30 days) for 2 visits (2 years of follow up total).
- Patients with disease progression at any time will come off treatment and receive standard of care therapy.

- Patients who come off treatment will follow up as required for gene transfer studies or as clinically indicated.

3.5.2 At each Response Evaluation, patients will undergo the following:

- Physical examination
- Chem 20 equivalent: (Sodium (Na), Potassium (K), Chloride (Cl), Total CO2 (Bicarbonate), Creatinine, Glucose, Urea nitrogen (BUN), Albumin, Calcium total, Magnesium total (Mg), Inorganic Phosphorus, Alkaline Phosphatase, ALT/GPT, AST/GOT, Total Bilirubin, Direct Bilirubin, LD, Total Protein, Total CK, Uric Acid).
- Complete Blood Count with differential and TBNK
- Toxicity assessment, including a review of systems.
- Serum, plasma, and peripheral blood lymphocytes.
- HSIL measurements and photographs will be taken for documentation of response.

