#### 6.3.4.3 Evaluation of Best Overall Response

The best overall response is the best response recorded from the start of the treatment until disease progression/recurrence (taking as reference for progressive disease the smallest measurements recorded since the treatment started).

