### 6.3.5 Duration of Response

Duration of overall response: The duration of overall response is measured from the time measurement criteria are met for CR or PR (whichever is first recorded) until the first date that recurrent or progressive disease is objectively documented (taking as reference for progressive disease the smallest measurements recorded since the treatment started).

Duration of overall CR: The duration of overall CR is measured from the time measurement criteria are first met for CR until the first date that progressive disease is objectively documented.

Duration of overall non-CR/non-PD: Non-CR/non-PD disease is measured from the start of the treatment until the criteria for progression are met, taking as reference the smallest measurements recorded since the treatment started, including the baseline measurements.

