## 8 STATISTICAL CONSIDERATIONS

The primary objective of this phase I trial is to determine the safe dose level of E6 TCR T cells for the treatment of vulvar HSIL. Secondary objectives include an assessment of the clinical responses in subjects receiving this treatment and exploratory analyses of translational research endpoints.

This is a phase I trial with a standard 3+3 design and two dose levels. The maximum number of patients required to determine the MTD on this trial is 12. Six additional patients will be evaluated at the MTD, for a maximum intended enrollment of 18 patients. To allow for patients who enroll but are not evaluable for the primary endpoint and screen failures, up to 200 patients total may be enrolled.

The expected accrual rate is 10-15 patients per year. It should therefore take 1.25-2 years to complete accrual of patients.

The clinical responses in 12 patients tested at the MTD may be used in the design of a subsequent phase II trial.

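### The progression rule sets a 5 mm length floor on a sum of areas; read as 5 mm², it does almost nothing to stop measurement error in small lesions being called progression

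*Combined protocol and SAP*

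**What the plan says.** Section 6.3.4.1 defines PD in target lesions as an "increase in sum of the product of the longest perpendicular diameters of target lesions" of at least 25%, measured from the smallest value on study, baseline included. It then sets a floor: "In addition to the relative increase of 25%, the sum must also demonstrate an absolute increase of at least 5 mm". New lesions also count as PD.

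Section 6.3.2 makes a lesion measurable at 5 mm or more in one dimension. All measurable lesions are targets, and there is no minimum second diameter, lesion number or total area. It asks for individual measurements in millimetres or decimals of a centimetre, and gives no unit for the sum. Section 6.3.3 adds: "Measurements will be recorded in metric notation using a ruler or calipers". No measurement error is stated, and no second visit is required to confirm PD on size.

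Four places depend on the PD call:

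- Section 6.3.4.3: "The best overall response is the best response recorded from the start of the treatment until disease progression/recurrence".
- Section 6.3.5: response duration runs "until the first date that recurrent or progressive disease is objectively documented".
- Section 3.5.1: "Patients with disease progression at any time will come off treatment and receive standard of care therapy".
- Section 8: "The clinical responses in 12 patients tested at the MTD may be used in the design of a subsequent phase II trial".

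**The concern.** A sum of products of two diameters is an area, so it cannot rise by 5 mm. An assessor has to choose a meaning. The two natural choices, 5 mm² of area or 5 mm of diameter, can give opposite calls on the same measurements.

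If 5 mm² is chosen, the floor is too low to act on nearly all eligible disease. PD is then decided by a 25% rise over the lowest value so far, with no confirmation. Because the reference is a running minimum, chance low readings lower the bar and false calls accumulate over visits.

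At stake are the secondary response endpoints. A patient who would first respond at month 3 loses that response if called PD at month 1 or 2. Response duration can be cut short. Some stable patients go to standard care up to two months early, since non-responders leave at month 3 in any case.

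**Working it through.** The plan states no figure that depends on this rule, so there is none to reproduce.

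**Inputs from the protocol.** Relative threshold 25% over nadir and floor of 5 mm (6.3.4.1); lesions from 5 mm (6.3.2); response visits at months 1, 2 and 3, and for responders through month 6 (3.5.1).

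**Assumed.** Independent normal error per diameter with SD 0.5 to 1.0 mm (0.25 mm as a favourable case), recording to the nearest 1 mm, square lesions.

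**1. The readings disagree.** From 5×5 to 6×6 mm the area goes from 25 to 36 mm² (+44%, +11 mm²). This is PD under a 5 mm² floor. The summed diameters rise by 2 mm and the longest by 1 mm, so it is not PD under a 5 mm diameter floor.

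**2. Where a 5 mm² floor acts.** It adds to the 25% rule only if 0.25 × S < 5, that is S < 20 mm². A 5×5 mm lesion, at 25 mm², is already above that.

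**3. A 1 mm error in both diameters.** The area rise is ((d+1)/d)² − 1:

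| d (mm) | 5 | 6 | 7 | 8 | 9 |
|---|---|---|---|---|---|
| rise | 44% | 36% | 31% | 27% | 23% |

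A single square lesion of 5 to 8 mm is therefore called PD. A lesion measured 10×10, then 6×6, then 7×7 mm goes from 36 to 49 mm² (+36%) and is PD, although 49 mm² is still under half of the 100 mm² baseline. A 1 mm error in only one diameter of a 5×5 mm lesion gives +20%, which is not PD.

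**4. False PD under the 5 mm² reading** (simulation, 200,000 patients per scenario, running minimum as reference):

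| Scenario | SD 0.5 mm | SD 1.0 mm |
|---|---|---|
| One lesion, stable, 3 visits: 5 mm | 57% | 79% |
| 10 mm | 7% | 46% |
| 15 mm | 0.5% | 20% |
| 20 mm | 0% | 7% |
| One lesion in partial response (PR; diameters ×0.6 from month 1), to month 6: from 10 mm | 54% | 90% |
| from 15 mm | 50% | 84% |
| from 20 mm | 13% | 64% |
| One lesion, late responder, PD at month 1 or 2: 5 mm | 41% | 59% |
| 10 mm | 4% | 30% |
| Three equal lesions, stable: 5 mm | 18% | 58% |
| 10 mm | 0.3% | 15% |
| 15 mm | 0% | 1.6% |
| Three equal lesions in PR: from 10 mm | 24% | 72% |
| from 15 mm | 2% | 39% |
| from 20 mm | 0% | 14% |
| Three stable lesions of 5, 10 and 15 mm | 0.1% | 11% |

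In the PR scenarios, 76% to 100% of first false PDs occur with the sum still at or below half of baseline. At SD 0.25 mm, one 5 mm lesion gives 13% (stable) and 9% (late responder); every other row is 3% or less.

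Without rounding, at SD 0.5 / 1.0 mm: stable 5 mm 46% / 76%, PR from 10 mm 58% / 91%, PR from 15 mm 21% / 77%.

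**5. A 5 mm floor on summed diameters.** A 25% area rise in a square lesion is √1.25 − 1 = 11.8% per diameter. The floor therefore acts while the summed diameters are below 5/0.118 = 42 mm: one lesion under about 21 mm, or three under about 7 mm each. For one lesion, false PD falls to 0.04% or less at SD 0.5 mm. At SD 1.0 mm it falls to 7% (stable), 15% (PR) and 4% (late responder). For three lesions, at SD 0.5 / 1.0 mm, it becomes 5% / 39% (stable 5 mm) and about 11% / 63% (PR from 10 mm). Stable 10 mm and PR from 15 mm are unchanged.

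**The case against.** The unit error does not itself produce the high rates. With the floor deleted, one stable 5 mm lesion goes only from 57% to 58% at SD 0.5 mm and from 79% to 80% at SD 1.0 mm. The 25%-over-nadir rule on small lesions is the source, and how much protection to add is a design choice. This stands as a statement of cause. It also shows that the floor, read as 5 mm², does not do the job of a floor.

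The rates depend on that reading. If 5 mm is taken as summed diameters, the problem largely disappears for one lesion. That is true, but nothing in the text selects that reading.

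The inputs are assumed, and some lean unfavourable. Section 6.3.2 requires accurate measurability and does not impose whole millimetres, and section 6.3.3 requires the same method each time, with photographs. Without rounding, PR from 20 mm at SD 0.5 mm falls from 13% to 4.5%. Eligibility includes multifocal and extensive disease, where the rates are lower. These points limit the size, not the contradiction.

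The consequences are modest. A PR recorded before a false PD still counts in best overall response, section 8 plans no analysis of response duration, and no frequency of late response is known. All of this stands.

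Finally, the remedy raises the effective threshold for a small single lesion: 5 to 7.5 mm is +125% in area, 10 to 12.5 mm +56%, 15 to 17.5 mm +36%. This is a real cost.

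**Conclusion.** The concern holds. The floor is wrong as written, and the 20 mm² break-even is exact; neither depends on any assumption. The false-PD rates rest on assumed error SDs, square lesions and rounding. They are large for one small lesion at SD 0.5 to 1.0 mm, and small at SD 0.25 mm or with larger or several lesions.

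The effect is confined to secondary response endpoints. Losing one late responder among the 12 patients at the maximum tolerated dose (MTD) would move the response rate by 1/12 = 8.3 percentage points; that is the size of one lost case, not an expected bias. The dose-limiting toxicity and MTD decisions are untouched, and with a single treatment course no study drug is withdrawn. The rule should be corrected before responses are read.

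**What to change.** Replace the floor sentence in 6.3.4.1 with:

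> For target lesions, PD requires a ≥25% increase over nadir in the sum of products AND a ≥5 mm increase over nadir in the sum of both recorded perpendicular diameters (longest plus perpendicular) of all target lesions. Each nadir is the smallest value of that sum on study, baseline included.

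New lesions and unequivocal non-target progression remain PD. The change needs no new measurement, because both diameters are already taken for the product.

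Two alternatives are worse. A floor on the longest diameter alone misses growth in width (20×8 to 20×16 mm) and full relapse of a small responding lesion (6×6 to 10×10 mm). An area floor of 25 mm² protects less: one stable 10 mm lesion still gives 6% / 41% at SD 0.5 / 1.0 mm, and PR from 15 mm 13% / 63%.

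The costs are:

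- Small true growth is called later: a single 5×5 mm lesion must reach about 7.5×7.5 mm, and a 10×10 mm lesion 12.5×12.5 mm.
- Narrow growth under 5 mm is not PD even if the area doubles (20×4 to 20×8 mm).
- Full regrowth of a very small single responder can add under 5 mm (5×5 to 3×3 to 5×5 mm adds 4 mm) and then relies on the term *recurrent* in 6.3.5. This applies to baselines below about 6.3 mm with ×0.6 shrinkage, or 8.5 mm at the PR limit.
- With several lesions the floor removes less false PD, and none once each of three is about 7 mm or more.

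If the sponsor prefers another floor, the text must still name its quantity and unit.

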#### 1.2.1 Vulvar high-grade squamous intraepithelial lesion (HSIL)

Vulvar HSIL is defined by the 2015 International Society for the Study of Vulvovaginal Disease (ISSVD) as an HPV-associated lesion of the vulva that has high malignancy potential. The term, vulvar HSIL, is equivalent to the previously used nomenclature of vulvar intraepithelial neoplasia, usual type [1]. It does not include low-grade squamous intraepithelial lesions without malignant potential such as condyloma acuminatum. It also does not include premalignant lesions that are not associated with HPV, which are classified as differentiated-type vulvar intraepithelial neoplasia. Multiple HPV types can cause vulvar HSIL but HPV-16 is the most prevalent [2]. Spontaneous regression of vulvar HSIL is rare, reportedly occurring in fewer than 1.5% of patients per year [3].

Patients with vulvar HSIL may present with symptoms of local itching, burning, or pain. Diagnosis is suggested by careful inspection of the lesion(s) and is confirmed by biopsy. Multicentric disease is common due to diffuse spread of HPV infection throughout vulvar epithelium. Vulvar HSIL transforms into vulvar squamous cell carcinoma (SCC) in 3 to 9% of patients. Therefore, all lesions require surveillance with physical exams and biopsies to rule out invasive cancer [4]. For lesions that do not regress, excision is required. The type of surgery depends on the extent and anatomic location of disease. Treatment of multifocal lesions, extensive disease, or lesions in proximity to the urethra, clitoris, or anus can result in deformity and functional impairment. Even with radical excision to negative margins, recurrence occurs in approximately 30% of patients [5]. Thus, surgery may be an unsatisfactory treatment option as it often fails to prevent disease recurrence, results in morbidity, and negatively impact psychological and sexual health [6].

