### 1.2.2 Studies of the natural history and treatment history of vulvar HSIL

Studies of the natural history and treatment of vulvar HSIL are scientifically limited as they are mostly retrospective and have small sample sizes. One systematic review reported that 6.5% of 3322 patients with vulvar HSIL progressed to develop an invasive vulvar carcinoma [3]. In untreated patients, invasive vulvar carcinoma developed in nine percent of subjects within one to eight years. Invasive cancers are treated with radical local excision or modified radical vulvectomy, depending on the tumor stage. Locally advanced cancers are treated with chemoradiation. Salvage surgery with pelvic exenteration and colostomy or ureteral diversion may be employed. Five-year survival for local, regional, and distant vulvar cancers are 86%, 54%, and 16% respectively. A study based on data from the United States reported the incidence of vulvar HSIL to be 2.86. per 100,000 women [7]. Immunotherapy for vulvar HSIL

Vulvar HSIL is caused by HPV infection, and HPV infections can be recognized and attacked by the immune system. Hence, immunotherapy is an attractive treatment strategy for vulvar HSIL. Topical immunotherapy with imiquimod, an immune response modifier that activates dermal dendritic cells through Toll-like receptor 7, has been reported to have response rates of 13-81%, but vulvar inflammation and pain limit its use and it is not currently FDA-approved [8]. Nonetheless, it is a treatment option that some patients should consider as an alternative to this protocol. Experimental vaccines have been tested for the treatment of vulvar HSIL. A clinical trial of a vaccine targeting HPV-16 E6 and E7 showed promising results in a single-arm phase II study [9]. This vaccine is experimental and not available outside of a clinical trial. The preventative vaccines for HPV (e.g. Gardasil and Cervarix) are highly effective at preventing HPV infections but not considered effective for the treatment of VIN [10].

[figure not shown]

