#### 5.1.3 Optional vulvar Biopsies

- Biopsies of vulvar lesions for clinical purposes will be obtained within 8 weeks prior to starting treatment if clinically indicated to rule out invasive cancer. Biopsies will be performed in the outpatient clinic under local anesthetic.
- Biopsies for research purposes will be obtained at baseline (within 8 weeks of starting treatment), 10 to 14 days after treatment, 27 to 34 days after treatment, and at the time the patient comes off-treatment (i.e. attains a complete response, experiences progression, or reaches the 6-month time point without a complete response). Clinically indicated biopsies may be obtained at any time by PI discretion if there is concern for invasive cancer.
- Biopsies for research will be performed with a standard punch biopsy instrument of up to 4 mm diameter. At each time point, up to 3 biopsies of HSIL lesions and up to 2 biopsies of adjacent normal tissue will be performed. A formalin-fixed paraffin embedded specimen will be transported to the NCI Laboratory of Pathology for review and archiving. The contact will be [name], [name], contact [contact]. Specimens will then be transported to the ETIB preclinical core for further processing and storage. They will be delivered to [name], Pre-Clinical Core lab; Attention [name], [name] contact [contact].
- Processing of biopsies will depend upon the amount of tissue obtained. Examples of processing may include OTC blocks, formalin-fixed paraffin embedding, snap freezing, placing in RNAlater or other required laboratory processing technique.
- Biopsies will not be performed if they are not technically feasible, if they will interfere with response assessment, or if a patient declines consent.

- Tissue samples will be coded and deidentified prior to transfer to the laboratory of [name], Genetics Branch, CCR for quantification of HPV DNA.
- Some of these samples will be archived and analyzed under another protocol 16-C-0061 (ETIB Tissue Procurement Protocol) if the subject is also enrolled on that study.

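### The response criteria do not cover invasive carcinoma in an existing lesion that is stable or shrinking, so such a patient can be scored PR or even CR instead of PD

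*Combined protocol and SAP*

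**What the plan says.** Under 6.3.4.1, target-lesion response depends on what can be seen and measured.

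- CR is "Disappearance of all target lesions. No appearance of new lesions".
- PR is a "decrease in the sum of the product of the longest perpendicular diameters of target lesions, taking as reference the baseline measurements" of 50% or more, with no new lesion and no index lesion more than 25% larger.
- PD is growth of at least 25% in the summed area with a minimum absolute increase, or a new lesion.

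For non-target lesions, 6.3.4.2 makes PD a new lesion or unequivocal progression, which has to reflect the non-target disease as a whole and not one lesion. The overall-response table in 6.3.4.3 only combines these categories.

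Histology enters once, in the note to 6.3.4.1 on a residual abnormality of uncertain meaning after regression. The note has two branches: "If HSIL is present in the pathology specimen the response will be considered less than complete", and "If HSIL is not present the response will be considered complete".

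Other sections do deal with invasive cancer. Section 1.2.1 says "Therefore, all lesions require surveillance with physical exams and biopsies to rule out invasive cancer". Section 2.1.2.7 excludes active invasive cancer at entry. Section 5.1.3 says "Clinically indicated biopsies may be obtained at any time by PI discretion if there is concern for invasive cancer". Section 3.5.2 collects the occurrence of vulvar cancer annually for five years. None of these is tied to a response category. Section 3.5.1 adds "Patients with disease progression at any time will come off treatment and receive standard of care therapy", without saying whether progression there means PD as defined in 6.3.4.

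**The concern.** Transformation to carcinoma is the main disease risk that the protocol describes, and the biopsies that could reveal it are already in the plan. Yet the scoring rules give it no category. If carcinoma arises inside a lesion that is already on record and is not growing, the patient's category follows from the measurements or from the absence of HSIL in the specimen. The worst disease outcome can then be recorded as a success.

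What is at stake is the secondary response endpoint. Section 8 says that responses in 12 patients at the MTD may inform the design of a phase II trial. Duration of response (6.3.5) has the same weakness, because it ends only at recurrent or progressive disease.

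**Working it through.** **Step 1: apply the rules as written.** In each case, invasive carcinoma is confirmed on biopsy. Unless stated otherwise, there is no new lesion and no PD on other grounds.

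| Finding | Category under 6.3.4 |
|---|---|
| Residual abnormality after regression; carcinoma, no HSIL; any non-target lesions gone | CR, by the second branch of the note |
| Same, but carcinoma and HSIL both present | Less than complete, but not PD |
| Target lesion 20 x 20 mm shrinks to 12 x 12 mm and contains carcinoma | PR |
| Existing target lesion with too little change for PR or PD, contains carcinoma | Non-CR/Non-PD |
| One existing non-target lesion, unchanged in size, contains carcinoma | Not clearly PD, given the overall-disease condition in 6.3.4.2 |
| Carcinoma appears as a new lesion | PD |
| Carcinoma with sufficient area growth | PD |

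The third row uses invented dimensions: 20 x 20 = 400, 12 x 12 = 144, and (400 - 144)/400 = 64%. This exceeds the 50% threshold whatever the histology. The gap is confined to the first five rows, and only the rows that end in CR or PR inflate the response rate.

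**Step 2: duration and best response.** Under 6.3.5 a response runs until recurrent or progressive disease is documented. Carcinoma in a stable or shrinking lesion meets no PD criterion, so the response need not end. Under 6.3.4.3 the best response recorded before progression is kept. If PR or CR was already recorded when carcinoma is found, a corrected PD definition would therefore change duration and not best response.

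**Step 3: the denominator.** Two dose levels with up to 6 patients each give 2 x 6 = 12 to find the MTD. Adding 6 gives 12 + 6 = 18 in total. At the MTD there are 6 + 6 = 12. All three figures match section 8.

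**Step 4: effect of one patient.** 1/12 = 8.3 percentage points. As an illustration with exact (Clopper-Pearson) intervals, 3/12 is 25.0% (95% CI 5.5 to 57.2%) and 2/12 is 16.7% (2.1 to 48.4%).

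**Step 5: how many patients.** Section 1.2.2 says "In untreated patients, invasive vulvar carcinoma developed in nine percent of subjects within one to eight years". Assume a constant hazard with that 9% accruing over T years, where T is between 8 and 1. The chance of at least one transformation among 12 patients in 6 months is 1 - 0.91^(12 x 0.5/T). For T = 8 this is 1 - 0.91^0.75 = 6.8%; for T = 1 it is 1 - 0.91^6 = 43.2%. These figures count every transformation. A misclassified responder must also meet PR or CR, and the documents give no figure for that joint event. On this assumption they are a ceiling for transformations arising in that window, not an estimate.

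**The case against.** The strongest reply has four parts.

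First, the protocol is not blind to cancer. Section 3.6.1 lists investigator discretion, 3.6.2 has a clause on changes in the patient's condition, and cancer occurrence is collected each year. A reader might infer that a patient with carcinoma is locked into responder follow-up. The documents do not support that. Removal is permitted, nothing in them bars cancer treatment, and with one cell infusion and at most two aldesleukin doses there is no study drug left to stop by any response visit. This part stands, but discretion to remove a patient does not change the recorded response.

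Second, section 1.2.2 itself describes patients as having progressed to carcinoma, so progression in 3.5.1 and 3.6.1 may naturally include it. That reading is reasonable, and it means one cannot claim that those provisions fail to apply. It does not repair 6.3.4, which sets out what counts as PD for scoring.

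Third, the CR route is narrow. It needs regression, an uncertain residue, an optional biopsy, and carcinoma without HSIL. This is true. The PR route needs only shrinkage and a biopsy that finds carcinoma.

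Fourth, the effect is small beside the uncertainty of a 12-patient rate, as the intervals above show. This also stands and limits the importance of the point. The error nevertheless runs in a known direction and is avoidable.

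**Conclusion.** The point holds as a fault in endpoint definition. The rules in 6.3.4 produce a wrong category when invasive carcinoma is found in an existing lesion that is stable or shrinking: CR by the histology note, PR by measurement, or Non-CR/Non-PD. Duration of response can be overstated for the same reason.

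The size is 8.3 percentage points of the MTD response rate for each reclassified patient, assuming that all 12 are evaluable under 6.3.1. Few such patients are to be expected, and their number cannot be derived from the documents. A reader might multiply the published transformation rates by the planned 18 patients and present the product as expected misclassifications. That would count patients who never meet PR or CR, and it would mix 18 patients with a response denominator of 12.

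Nor do the documents support reading this as a flaw in the primary objective: the DLT definition and the dose-escalation rules do not use response. The conclusion rests on a literal reading of 6.3.4, which is how a prespecified criterion should be applied.

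**What to change.** Change the endpoint definition only.

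1. In the note to 6.3.4.1, make a response complete only when the specimen shows neither HSIL nor invasive carcinoma.
2. In 6.3.4.1, 6.3.4.2 and the overall-response table, state that histologically confirmed invasive vulvar carcinoma, from any biopsy already planned or clinically indicated, is PD for response and for duration of response, whatever the measurements.
3. Reconcile the word progression in 3.5.1 and 3.6.1 with that definition. The sponsor should say whether it means PD under 6.3.4 or something broader. No removal or treatment rule is proposed here.

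A separate serious-event provision is largely unnecessary, because 7.1.5 and 7.2.2 already cover most of that ground.

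The cost is protocol wording. No procedure, biopsy, patient or sample-size figure changes. The downside is that the reported response rate or duration could be slightly less favourable.
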